Cardiac surgery residents' learning curve of intraoperative transit-time flowmetry and high-frequency ultrasound in coronary artery bypass surgery: the LEARNERS study.

12/04/2024

ABSTRACT

Transit-time flowmetry (TTFM) allows grafts quality assessment during coronary artery bypass surgery by measuring the flow volume through them. Recently the intraoperative epicardial high-frequency ultrasound (HFUS) was introduced, with the possibility of capturing bidimensional images of the anastomoses. When combined, these two techniques provide high diagnostic yield reaching a positive predictive value of 100 percent.

Despite current guidelines recommend the employment of TTFM and HFUS, they remain largely underused probably because of limited information and the lack of standardization. Furthermore, surgeons must overcome a learning curve to handle both techniques properly, but few data are available according the current literature.

The main purpose of this study is to evaluate the complexity of HFUS and TTFM learning curve. This is a prospective, observational, monocentric cohort study. Adult patients undergoing coronary artery bypass surgery will be enrolled.

BACKGROUND

During coronary artery bypass surgery, it is essential to verify grafts patency and functioning. Indeed, this has important consequences in the perioperative period and an impact on patient long-term prognosis (1,2).

Since the second half of the 1990s, this intraoperative quality control is possible thanks to the transit-time flow measurement (TTFM) that evaluates the flow volume through the grafts.

The evaluation of the coronary grafts by TTFM allows to acquire the following parameters:

- Mean flow (ml/min): it is influenced by multiple factors including the size and quality of the graft, the size and quality of the coronary target, the quality of the anastomosis, the run-off of the distal coronary vascular territory, the hemodynamic condition of the patient, the presence of competitive flow between grafts pertaining to the same territory.

According to currently guidelines, the average flow should be above 20 ml/min (3,4).

- Pulsatility index (PI): calculated as [(maximum flow - minimum flow)/average flow] through 5 cardiac cycles. It represents an estimate of resistance to flow. It can be influenced by multiple factors: anastomosis quality, coronary stenosis after the anastomosis, competitive flow.

Literature data suggest that an ideal value would be < 3 (4).

- Backward flow (BF - percentage): it represents the percentage of flow directed from the native coronary artery to the graft during a cardiac cycle. It may indicate the presence of competitive flow between the graft and the coronary target; studies that evaluated the association between BF percentage and angiographic patency of remote graft concluded that this parameter can be considered a predictor of patency of anastomosis with an identified cut-off of 3 percent of the total flow; (5) practically, a retrograde flow area >3 percent of the total graft flow area represents a risk factor for failure.

- Diastolic filling (DF - percentage): this is a parameter that describes the mode of flow distribution according to the phase of the cardiac cycle (systole/diastole); it provides an estimate of the diastolic flow within the graft, considering that:

1) the prevalence of diastolic flow is a distinctive feature of the left coronary circulation in which coronary resistances are higher during systole for higher transmural pressure;

2) the right coronary artery supplies the right ventricular myocardium in both systole and diastole; for this reason, in this territory a DF percentage is accepted around 50 percent and it may change in case of right coronary hyper-dominance.

The correct interpretation of the TTFM requires an integration of all these parameters and their analysis also in light of the result of the intraoperative HFUS, an intraoperative imaging technique introduced in 2009. Throughout a sterile probe, this technique consents to acquire bidimensional images of the anastomoses and, in addition to TTFM, serves as a benchmark of their patency and correct shape.

Once the data obtained throughout TTFM and HFUS are combined, the surgeon can consider the graft as functioning and patent in the long term. Indeed, recent studies found out that the positive predictive value of TTFM rose from 10 percent to 100 percent when HFUS was added to the intraoperative assessment (6, 7).

Our operative unit adopted this protocol and systematically applies it to every coronary artery bypass graft performed, both in isolated and combined procedures.

Although last European Guidelines on myocardial revascularization recommended intraoperative flowmetry and ultrasound (Class IIa, evidence level B) (1), their use remains substantially limited due to the lack of familiarity with instruments and results interpretation (8).

Furthermore, surgeons must overcome a learning curve to handle both techniques properly, but few data are available according the current literature. The ability of mastering TTFM and HFUS comes gradually but incessantly; constant learning and self-assessment make surgeons continuously improve (9).

Regarding TTFM, when correctly applied it can provide invaluable information about graft flow; however, proper handling technique is paramount. (6) A learning curve is required to interpret it correctly and, in particular at the beginning, diagnostic errors and unnecessary graft revision cannot be excluded. (8)

The basics of TTFM are easy to learn, while the nuances come gradually but constantly; with continued routine use, one begins to appreciate subtle changes of coronary flow in order to detect flow competition or the difference between a perfect graft and a less-than-perfect but functioning one. (9, 10). In light of this, some authors suggest starting first with use of TTFM, use on every graft at least 4 times/graft and continue with this modality alone for at least 6 months. (9)

Instead learning to master the HFUS presents bigger technical challenges. Performing ultrasound on a moving target can actually be more difficult than performing the anastomosis itself, due to the need of maintaining stable and optimal acoustic contact between the ultrasound probe and the target without distorting the anastomosis. (9, 11, 12)

Detractors of this technique have highlighted as its major limit the lack of standardization because of its operator dependency. (13) Some authors though compared two experienced surgeons letting them observe and independently evaluate 120 consecutive anastomoses; having obtained identical results, they proved how, in experienced hands, epicardial ultrasound evaluation appears reproducible and operator independent. (14) Therefore, in order to gain experience, it is mandatory to apply HFUS routinely, starting with selected patients and after proper training from peers or radiologists. (13, 15) Despite HFUS learning curve requires more patience and attention to detail that TTFM, the basics can be learned in about 10–20 grafts. (9, 10)

STUDY OBJECTIVES

Primary objective

Evaluate the complexity of cardiac surgery residents' learning curve for grafts quality assessment with TTFM and HFUS.

Secondary objectives

- Evaluate the complexity of cardiac surgery residents' learning curve for grafts quality assessment with HFUS as isolated technique.
- Evaluate the complexity of cardiac surgery residents' learning curve for grafts quality assessment with TTFM as isolated technique.

STUDY DESIGN AND DURATION

This is a prospective, observational, monocentric cohort study in which adult patients undergoing coronary artery bypass surgery will be enrolled.

The study will last four months: three months for patients enrollment and data collection and one month for statistical analysis and scientific paper writing.

The trial will start after obtaining favourable opinion from the local Ethics Committee and could be considered completed when all the eight cardiac surgery residents involved have reached primary endpoint.

INCLUSION CRITERIA

- Age ≥ 18 years old;
- Written informed consent;
- Indication to CABG surgery (both «on-pump» and «off-pump»);
- Stable angina, unstable angina or acute coronary syndrome without ST elevation (NSTEMI).

EXCLUSION CRITERIA

- Age ≥ 18 years old;
- Written informed consent;
- Indication to CABG surgery (both «on-pump» and «off-pump»);
- Stable angina, unstable angina or acute coronary syndrome without ST elevation (NSTEMI).

STUDY PROCEDURES

All patients with coronary artery disease and an indication for surgical revascularization (coronary artery bypass grafting) who meet the above-described inclusion and exclusion criteria will be enrolled by signing the informed consent the day before surgery.

Patient data (anamnestic data, surgery description, *intraoperative echographic and flowmetric measurements*) will be recorded in a dedicated database. All data recorded in the database are commonly acquired for all patients undergoing this type of surgery and no further examinations will be performed for patients included in the trial.

The study will involve cardiac surgery residents with different levels of training and an expert cardiac surgeon who acts as supervisor and benchmark. Each resident will sign a dedicated informed consent form in the presence of a doctor foreign to the study protocol (Cardiac Surgery ward cardiologist). The residents will be “blinded” about the trial objective and the adopted score system. They will undergo a specific training including a quick lesson and a practical workshop to familiarize with the equipment.

During surgery, every graft will be evaluated through transit time flowmetry (TTFM) and intraoperative ultrasound control (HFUS).

In details, the ultrasound control is carried out through a dedicated sterile ultrasound probe connected to a machine (MiraQ - MEDISTIM) as soon as each anastomosis is completed. The result of the evaluation is recorded together with surgery data. This evaluation is intended to confirm the correct realization of the anastomosis and provides a proof of its patency.

Once each graft is completed, the resident will be given 60 seconds to acquire two HFUS recordings (short and long axis). After that, the supervisor will perform his personal recording which will stand as benchmark. The following items will be evaluated:

- A) Long axis recording acquired within 60 seconds [YES → 1] [NO → 0]
- B) Long axis recording judged as suitable by the supervisor [YES → 1] [NO → 0]
- C) Short axis recording acquired within 60 seconds [YES → 1] [NO → 0]
- D) Short axis recording judged as suitable by the supervisor [YES → 1] [NO → 0]

E) Correct interpretation of the anastomosis as adequate or inadequate [YES → no penalty] [NO → total score becomes 0 and the resident isn't allowed to perform TTFM]

Each resident will be given a HFUS-related score from a minimum of 0 to a maximum of 4. Whenever one of the recordings will be judged as non-suitable by the supervisor and consequently useless for a correct interpretation of the anastomosis (score 0 for items A and/or C), item E won't be evaluated and the HFUS will be given a total score of 0.

Next step will be the TFM evaluation, which is carried out through a specific sterile device connected to the same machine (MiraQ - MEDISTIM) once the patient has been weaned from the cardiopulmonary bypass and before protamine administration. This recording is performed under EKG and pressure-controlled conditions. Although there is no general agreement on the optimal mean arterial pressure at which the measurement has to be recorded, we will adopt the standard used in the REQUEST study protocol (16), that is an average pressure of 80 mmHg.

The resident will acquire the TTFM recording after each graft is completed. To make the comparison as accurate as possible, the resident will perform TTFM evaluation on one graft at a time and successively the supervisor will do the same for each graft (making sure that delta between the pressure during the two recordings is lower than 10 percent and that no drug has been administered). The following items will be evaluated:

F) Time necessary to acquire the measures [$< 30 \text{ sec} \rightarrow 1$] [$> 30 \text{ sec}, < 60 \rightarrow 0.5$] [$> 60 \text{ sec} \rightarrow 0$]

G) Need for multiple measurements before the final one: [$> 2 \rightarrow 0$] [$1 \rightarrow 0.5$] [$0 \rightarrow 1$]

H) Need to change probe dimensions: [NO $\rightarrow 0$] [YES $\rightarrow 1$]

I) ACI [delta between resident and supervisor measurements $< 10\% \rightarrow 1$] [$> 10\%, < 20\% \rightarrow 0.5$] [$> 20\% \rightarrow 0$]

L) Mean Flow [delta between resident and supervisor measurements $< 10\% \rightarrow 1$] [$> 10\%, < 20\% \rightarrow 0.5$] [$> 20\% \rightarrow 0$]

M) Pulsatility Index [delta between resident and supervisor measurements $< 10\% \rightarrow 1$] [$> 10\%, < 20\% \rightarrow 0.5$] [$> 20\% \rightarrow 0$]

N) Backward Flow [delta between resident and supervisor measurements $< 10\% \rightarrow 1$] [$> 10\%, < 20\% \rightarrow 0.5$] [$> 20\% \rightarrow 0$]

O) Diastolic Filling [delta between resident and supervisor measurements $< 10\% \rightarrow 1$] [$> 10\%, < 20\% \rightarrow 0.5$] [$> 20\% \rightarrow 0$]

P) Correct interpretation of the graft quality as working [YES \rightarrow no penalty] [NO \rightarrow total score becomes 0]

Each resident will be given a TTFM-related score from a minimum of 0 to a maximum of 8.

The final score for each graft will be the sum of the two scores (HFUS and TTFM), from a minimum of 0 to a maximum of 12.

The same procedure will be repeated for each graft performed during the surgery.

Each resident will continue until reaching a ratio between total score and number of evaluated anastomoses of 11.

END-POINTS

Primary end-point

Number of anastomoses needed to reach a ratio (total score/n. of anastomoses) ≥ 11

Secondary end-points

- Number of anastomoses needed to reach a ratio (HFUS score/n. of anastomoses) = 4
- Number of anastomoses needed to reach a ratio (TTFM score/n. of anastomoses) ≥ 7

STATISTICAL ANALYSIS AND SAMPLE SIZE CALCULATION

Sample size calculation

Our cardiac surgery unit performs between 5 and 10 coronary artery bypass grafts surgeries per week on average. Considering the inclusion and exclusion criteria and assuming that some patient may not give their informed consent, we expect to enroll 4 patients per week. Considering that the involved residents (8 in total) will take part to the procedures in turn and that we estimate around 10 surgeries to become autonomous, we estimate to enroll 80 patients during a period of 3 months.

Statistical analysis

Data will be collected in a specific database (Microsoft Excel worksheet). The Kolgomorov-Smirnov test was used to check for variables distribution. Continuous variables with a normal distribution are summarized by mean and standard deviation. Continuous variables with a non-normal distribution are expressed with median and interquartile range.

Categorical variables are reported as absolute frequency distribution and percentage. Continuous data are analyzed using the unpaired t-test or the Mann – Whitney test according to their distribution. Categorical data are compared with the Fisher's exact test. Statistical findings were considered significant if p value was less than 0.05. Statistical analysis will be performed with the statistic software SPSS (IBM).

BIBLIOGRAPHY

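### The three-month window and the all-eight completion rule are not reconciled, and the primary end-point gives no value to a resident who has not reached a ratio of 11

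*Combined protocol and SAP*

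**What the plan says.** Study Design and Duration gives "three months for patients enrollment and data collection and one month for statistical analysis and scientific paper writing". The same section adds that the trial "could be considered completed when all the eight cardiac surgery residents involved have reached primary endpoint".

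Study Procedures sets the rule for the individual: "Each resident will continue until reaching a ratio between total score and number of evaluated anastomoses of 11". The primary end-point is "Number of anastomoses needed to reach a ratio (total score/n. of anastomoses) ≥ 11". The secondary end-points are "Number of anastomoses needed to reach a ratio (HFUS score/n. of anastomoses) = 4" and "Number of anastomoses needed to reach a ratio (TTFM score/n. of anastomoses) ≥ 7".

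The sample size section expects 4 enrolled patients per week, eight residents taking turns, about 10 surgeries for a resident to become autonomous, and 80 patients in three months. The statistical analysis section offers mean with standard deviation or median with interquartile range, the unpaired t-test or Mann-Whitney test, and Fisher's exact test. The document states no maximum number of anastomoses per resident, no value for a resident who has not reached 11, and no method for censored counts.

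**The concern.** One rule ends data collection by the calendar. The other ends the study by an event that must occur in all eight residents. They agree only if the slowest resident reaches 11 within three months. Residents are to have different levels of training, so slow learners are foreseeable.

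The primary objective is how hard the learning curve is. The residents with the most to say about that are the ones who take longest, and the end-point as worded exists only for those who arrive. Dropping the others biases the summary towards an easy technique. Waiting for them leaves the study without an end date.

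A secondary matter is that each resident's scoring stops on the composite result, which treats the two techniques unequally. The composite threshold guarantees the TTFM criterion but not good HFUS performance.

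**Working it through.** **1. The plan's own figure.** Inputs from the sample size section: 8 residents and about 10 surgeries each. 8 × 10 = 80 patients, so the stated number reproduces.

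**2. Does it fit the window?** Inputs: 4 patients per week (sample size section) and three months, taken as 12 to 13 weeks.

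- Patients in the window: 4 × 12 = 48; 4 × 13 = 52.
- Shortfall against 80: (80 − 48)/80 = 40%; (80 − 52)/80 = 35%.
- Surgeries per resident: 48/8 = 6.0; 52/8 = 6.5, against about 10.
- Time needed for 80 patients: 80/4 = 20 weeks, about 4.6 months.
- Rate needed for 80 in the window: 80/13 = 6.2 to 80/12 = 6.7 per week.

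The window is too short even for a resident who needs exactly the assumed 10 surgeries.

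**3. What a cumulative ratio of 11 demands.** The maximum per graft is 12. Suppose m scores equal s before the threshold is reached and all others are 12. Then 12(n − m) + ms ≥ 11n, which gives n ≥ m(12 − s).

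| Low scores | Minimum anastomoses |
|---|---|
| one 0 | 1 × 12 = 12 |
| two 0s | 2 × 12 = 24 |
| three 6s | 3 × 6 = 18 |

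Zeros are built into the scoring: a wrong interpretation under item E zeroes the score and bars the TTFM step. The documents do not give anastomoses per surgery. Assuming 2 to 4, 6.0 to 6.5 surgeries yield 12 to 26 anastomoses per resident, and 10 surgeries yield 20 to 40. One or two zeros can therefore use up the whole window. This step needs no assumed learning curve.

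**4. How many would reach 11?** This cannot be fixed from the documents. An illustrative simulation (4,000 residents per scenario) scored HFUS as 4 or 0, scored TTFM in half-points, and always awarded the item H point. The chance of full HFUS marks rose from 0.80 to 0.99 (fast), 0.60 to 0.97 (middle) or 0.40 to 0.95 (slow). The chance of each TTFM half-point rose from 0.85 to 0.98, 0.75 to 0.97 or 0.65 to 0.95. The learning constants were 4, 6 and 10 grafts.

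| Assumed learner | Reach 11 by 20 anastomoses | Reach 11 by 40 |
|---|---|---|
| fast | 98% | 100% |
| middle | 36% | 87% |
| slow | 4% | 4% |

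The range runs from nearly all to almost none, so no single percentage should be quoted as the size of the problem.

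**5. What the stop at 11 implies for each technique.** HFUS is at most 4, so a composite of 11 forces TTFM ≥ 11 − 4 = 7. TTFM is at most 8, so it forces HFUS only ≥ 11 − 8 = 3. For example, four grafts with one HFUS zero and everything else perfect give (12 × 4 − 4)/4 = 11.0, with an HFUS ratio of 12/4 = 3.0. Scoring then ends.

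**6. The HFUS end-point itself.** Scores are capped: "Each resident will be given a HFUS-related score from a minimum of 0 to a maximum of 4". A cumulative mean equal to the cap requires every score to be 4. The criterion is therefore met at the first anastomosis or never.

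**The case against.** **Flexible wording.** The completion sentence says the study could be considered complete, and three months is a planned duration, so a reader should not infer that the calendar is fixed or that completion can occur in only one way. Nor must slow learners lose their outcome: if the completion rule prevails, everyone who eventually reaches 11 has an exact count. This stands. The two harms are alternatives, and the defect is that the plan does not choose. The plan also does not say that it will summarise reachers alone; that is a consequence to guard against.

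**Accrual.** The unit performs 5 to 10 procedures per week, so 6.2 to 6.7 enrolments per week is not impossible. But the plan, after allowing for eligibility and consent, expects 4.

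**Analysis.** A median or rank test could place non-reachers last by convention. The plan states no such convention, and a mean or t-test cannot use one.

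**HFUS.** A reader might infer that stopping at 11 costs residents the HFUS end-point, or that longer scoring would restore it. Step 6 shows otherwise: the stop shortens the HFUS score series but cannot change an end-point already decided at the first anastomosis. In addition, item H as printed gives 0 when no probe change is needed. If that point were never earned, the maximum would be 11, reaching 11 would require HFUS 4 throughout, and the shortening would disappear. Any lost half-point would then put 11 out of reach, so there would be more non-reachers.

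**Lucky runs.** A reader might also infer that a brief good run could trigger the stop. The ratio averages from the start: after a first score of 6, five straight 12s are needed. A chance crossing is plausible only in the first few anastomoses.

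**Conclusion.** Wrong as written. The two end rules are unreconciled, and the primary end-point and its analysis make no provision for a resident still below 11.

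The firm part of the size comes from the plan's own figures: 48 to 52 patients in place of 80, and 6.0 to 6.5 surgeries per resident in place of about 10. The scoring rules add that one zero before the threshold requires at least 12 anastomoses and two require at least 24. How many of the eight would fall short depends on learning curves and anastomoses per surgery that the documents do not give.

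The HFUS point is secondary. Provided the item H point is earned, a resident can stop with an HFUS ratio as low as 3.0, which shortens that series. The HFUS end-point has a separate fault in its criterion.

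**What to change.** 1. State one end rule: the end of a stated data-collection period. Delete completion conditional on all eight residents reaching the end-point.
2. Make duration and accrual agree. At 4 patients per week, 80 patients need 20 weeks; otherwise plan for 48 to 52 patients, or justify 6.2 to 6.7 per week.
3. Define the primary end-point as the anastomosis number at which the ratio first reaches 11, censored at the resident's last scored anastomosis.
4. Report the number reaching it out of 8 and a Kaplan-Meier median on the anastomosis-count scale.
5. Redefine the HFUS criterion so that it can be met after an early miss, for example over a run of consecutive anastomoses. Longer scoring alone will not repair it.

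Continuing to score residents after they reach 11 is optional. It would give a fuller HFUS series, but cases are shared in turn, so it takes cases from slower residents and increases censoring.

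The end-rule and analysis changes cost protocol wording and a standard censored summary. Keeping 80 patients at 4 per week also costs about seven to eight more weeks (20 − 13 to 20 − 12). The result may read as x of 8 reached, and the median may not be estimable if fewer than half reach 11.

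### The bar of 11 out of 12 is only partly tied to the expert: five points are scored against fixed limits with no supervisor value for the same graft, so their attainability and the effect of graft difficulty cannot be checked

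*Combined protocol and SAP*

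**What the plan says.** Study Procedures describes the reference operator as "an expert cardiac surgeon who acts as supervisor and benchmark". After the resident's 60-second ultrasound attempt on a graft, "After that, the supervisor will perform his personal recording which will stand as benchmark". For flowmetry the supervisor also repeats the measurement on each graft, with limits on pressure change and drug administration between the two readings.

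Only residents are scored: "Each resident will be given a HFUS-related score from a minimum of 0 to a maximum of 4", and "Each resident will be given a TTFM-related score from a minimum of 0 to a maximum of 8". The items fall into two groups.

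- **Resting on the supervisor.** B and D (suitability of each view, as the supervisor judges it) and I, L, M, N and O (percentage difference from the supervisor's reading).
- **Resting on fixed limits.** A ("Long axis recording acquired within 60 seconds"), C ("Short axis recording acquired within 60 seconds"), F ("Time necessary to acquire the measures", with cut-offs at 30 and 60 seconds), G (number of repeat measurements) and H (probe size changed; printed as NO = 0, YES = 1).

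Items E and P, on interpretation, carry no points but can set a score to zero. Under End-points, the primary end-point is the number of anastomoses needed for the average total score to reach at least 11. No section explains why 11 was chosen. None provides for recording the supervisor's acquisition times, repeats or probe changes. The Statistical analysis section lists unadjusted two-group tests, with no graft, target or surgical-technique factor.

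**The concern.** The study's result is a count of grafts to a threshold. To read that count as a learning curve, one must know that a skilled operator can hold the threshold on these grafts, and that a slow approach reflects the resident rather than the grafts. For seven points the supervisor supplies that reference. For the other five nothing does, although the supervisor performs the same acquisitions on the same graft.

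Difficulty is likely to vary. The Background describes ultrasound on a moving target as technically demanding, and the inclusion criteria admit both on-pump and off-pump surgery. The pressure and drug conditions protect only the agreement items. A high count could therefore mean slow learning, a run of hard grafts, or a bar that experts do not hold either. Study Design and Duration also makes completion depend on all eight residents reaching the bar.

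**Working it through.** **1. The plan's own totals.** HFUS: A + B + C + D = 4. TTFM: F + G + H + I + L + M + N + O = 8. Total 12. These match the stated maxima.

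**2. Split by reference.** Supervisor-based: B, D, I, L, M, N, O = 7. Fixed limits: A, C, F, G, H = 5. With all 7 supervisor-based points earned, holding 11 needs 11 − 7 = 4 of the remaining 5 on average. The loss allowed is 12 − 11 = 1 point per graft.

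**3. The zero rule adds weight.** Study Procedures sets the HFUS score to 0 for a 0 on A and/or C. Read that way, one missed view costs 4 points, and up to 4 + 3 (F, G, H) = 7 of 12 points depend on items without an expert reference. A graft with HFUS 0 and full TTFM scores 8, and three perfect grafts are then needed to return to the bar: (8 + 36)/4 = 11. The rule's wording is not settled, however. It speaks of unsuitable recordings (B and D) but cites A and C.

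**4. What an expert might lose.** The documents give no rates, so all shares below are assumptions:

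- f = share of grafts with TTFM time of 30–60 s (−0.5)
- r = share with one repeat (−0.5)
- v = share with a view missed at 60 s (−4 under the zero rule)
- h = share on which the H point is earned

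The operator is taken as perfect on the other seven points apart from the zero rule. Mean loss = 0.5f + 0.5r + 4v + (1 − h).

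| f = r | v | h = 1 | h = 0.5 | h = 0 |
|---|---|---|---|---|
| 0.2 | 0.02 | 0.28 | 0.78 | 1.28 |
| 0.3 | 0.05 | 0.50 | 1.00 | 1.50 |
| 0.5 | 0.10 | 0.90 | 1.40 | 1.90 |
| 0.6 | 0.15 | 1.20 | 1.70 | 2.20 |

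First row: 0.1 + 0.1 + 0.08 = 0.28. A loss above 1 means that a long-run mean of 11 cannot be held. If a missed view cost only its own point, 4v would become v, and the h = 1 column would read 0.22, 0.35, 0.60 and 0.75. The formula leaves out the full-point losses for times over 60 s and for more than two repeats, which would add to the loss.

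**5. Item H.** As printed, an operator who never needs another probe loses 1 point on every graft. The maximum is then exactly 11, with no other loss allowed. So H can decide attainability alone, and it runs opposite to A, C, F and G: a graft that calls for a probe change gains the point.

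**The case against.** The strongest reply is that fixed limits are a legitimate absolute standard. The stated objective is the complexity of the learning curve, not equivalence with an expert, and averaging over grafts with residents in rotation smooths out some of the difficulty. This stands in part: fixed limits are not an error. But the plan neither presents them as an absolute standard nor justifies them, and averaging is not adjustment.

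The second reply concerns the remedy. The supervisor always goes second, after the resident has located the views and perhaps settled the probe size. The supervisor's values may look better than they would going first, and resident minus supervisor mixes skill with order. This stands. It makes the values a best-case reference, but still a useful one.

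A reader might also infer more than the documents support:

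- **That the bar has no link to the expert.** It has: without the seven supervisor-based points a resident can score at most 5.
- **That experts cannot hold 11.** This is not shown. Every rate is assumed, and with H always earned only the most extreme row exceeds 1 point.
- **That difficulty always counts against the resident.** For H as printed it does not.
- **That a mean below 11 means never reaching the end-point.** The end-point is met once the running average reaches 11, which can happen early by chance. With f = r = 0.2, v = 0.05, h = 0 and independent losses, the mean loss is 0.1 + 0.1 + 0.2 + 1 = 1.40. Yet the first graft scores 11 with probability 0.95 × 0.8 × 0.8 = 0.608.

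**Conclusion.** The point holds as a gap in reference data, not as a demonstrated failure of the end-point. Five of 12 points, of which at least 4 on average are needed, have no expert value for the same graft, and the plan gives no basis for 11. Whether an expert could hold 11 turns on rates that the plan does not measure: the assumed cases give losses on both sides of the 1 point allowed. The split of points is exact. The losses rest on the assumed shares, on reading the zero rule as applying to missed views, and on the direction of H. On A, C, F and G, difficulty shared with the expert is charged in full to the resident, and no planned analysis separates it. This is a worthwhile, inexpensive improvement to interpretation.

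**What to change.** 1. Reconcile the scoring of item H and the wording of the HFUS zero rule before enrolment.
2. For every graft, record the supervisor's time to each HFUS view, TTFM acquisition time, number of repeats and probe changes.
3. Report the supervisor's mean score on A, C, F and G, and on H once reconciled, beside the residents'.
4. Add a secondary learning curve for these items: resident minus supervisor on the same graft.
5. Leave the primary end-point unchanged, give the reason for choosing 11, and report whether the supervisor's own losses would leave a mean of 11 attainable, taking 1 point per graft as the limit.
6. State the order effect. If even these best-case losses exceed 1 point per graft, the bar cannot be held as a long-run mean. Losses below 1 do not prove that an expert going first would hold it.

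**Cost.** A few more database fields per graft. No extra acquisitions or patients are needed, because the supervisor already repeats both techniques. Someone must time the supervisor, who must accept being timed. The supervisor cannot be scored on I to O without a second expert, and this change does not ask for that.
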